3.8.3.2 Documenting Reasons for Treatment Discontinuation

A subject may discontinue the IMP for a number of reasons including those listed below.

- Reasons related to AEs:
 - Legal representative or subject decides to discontinue because of annoyance or discomfort due to a nonserious AE which is not otherwise determined to be an undue hazard
 - Continuing treatment with the IMP places the subject at undue risk as determined by the investigator or subinvestigator
- Serious adverse event (SAE)
- Other safety concerns or AEs that may possibly be related to the IMP
- Death
- Lost to follow-up
- Poor IMP compliance
- Pregnancy (see [Section 5.5](#))
- Major protocol deviations
- Withdrawal of informed consent (complete written consent to withdrawal form)

- Termination of all or part of the trial by the sponsor
- Other reasons unrelated to medical condition
(including the case where the subject was found to deviate from any of the inclusion criteria or to meet any of the exclusion criteria, after start of IMP administration)

If treatment is discontinued due to an AE, the investigator or subinvestigator will follow up the event according to [Section 5.7](#).

3.8.3.3 Withdrawal of Consent

All legal representatives and subjects have the right to withdraw their consent from further participation in the trial at any time without prejudice. Legal representatives and subjects cannot withdraw consent for use of data already collected as part of the trial, but only for future participation. The investigator or subinvestigator can also discontinue a subject's participation in the trial at any time if medically necessary. Unless the legal representative provides his/her written withdrawal of consent or there is other written documentation by the investigator confirming the legal representative's verbal intent to completely withdraw from the trial, the subject should be followed for all protocol-specified evaluations and assessments, if possible.

Complete withdrawal of consent requires the legal representative's or subject's refusal of ALL of the following procedures of follow-up (these procedures of follow-up will also be noted in the trial ICF).

- Participation in all follow-up procedures specified in the protocol (whether in-site, by telephone, or by an in-home visit)
- Participation in a subset of protocol specified follow-up procedures (by a frequency schedule and method, as agreed by legal representative and trial personnel)
- Contact of the legal representative and subject by trial personnel, even if only by telephone, to assess current medical condition, and obtain necessary medical or laboratory reports relevant to the trial's objectives
- Contact of alternative person(s) who have been designated in source records as being available to discuss the subject's medical condition, even if only by telephone, mail, or e-mail (eg, family, legal representative, friend, neighbor, or physician)
- Access to medical information from alternative sources (eg, hospital/clinic medical records, referring doctor's notes, public records, dialysis, transplantation or vital registries, social media sources)

Withdrawal of consent is a critical trial event and therefore should be approached with the same degree of importance and care as is used in initially obtaining informed consent. The reasons for a legal representative's intended withdrawal need to be completely

understood, documented, and managed to protect the rights of the subject and the integrity of the trial. A legal representative may initially express their desire to discontinue IMP administration, which is not equivalent to a complete withdrawal of consent for further participation (see [Section 3.8.3.1](#)). A legal representative may, however, indicate that further trial participation is creating a burden on their work or social schedule. Therefore, the investigator or subinvestigator should follow the procedures outlined in [Section 3.8.3.2](#) to determine if the subject can continue participation in the trial if modifications to his/her treatment and/or schedule of assessments can be accommodated. Only legal representatives who withdraw their permission for all of the above degrees of follow-up are considered to have completely withdrawn their consent for subject's participation in the trial.

3.8.3.4 Procedures to Encourage Continued Trial Participation

In all cases of impending IMP discontinuation or consent withdrawal, the investigator or subinvestigator will meet/phone and discuss with the legal representative about options of continuing in the trial, preferably on therapy. The investigator or subinvestigator should ensure understanding and documentation of the reasons for the subject's desire to withdraw consent.

3.9 Screen Failures

A screen failure subject is one from whom informed consent is obtained and is documented in writing (ie, a legal representative signs an ICF), but who is not started on treatment.

A subject for whom a legal representative signs an ICF, but who is not started on treatment is permitted to be re-screened as specified in [Section 3.4.3](#).

For a subject who meets the definition of screen failure, the following items will be recorded in a CRF for screen failure.

- Date of investigation
- Date on which the subject was determined to be a screen failure
- Date of informed consent
- Birth date
- Gender
- Race
- Compliance with the inclusion criteria (Record the criterion number the subject did not meet, if any)

- Deviation from the exclusion criteria (Record the criterion number the subject met, if any)
- Reason for screen failure

3.10 Definition of Completed Subjects

Subjects who have received IMP administration at evaluation dose (see [Section 7.4](#)) for 3 days will be defined as trial completers.

3.11 Definition of Subjects Lost to Follow-up

Subjects who cannot be contacted on or before the day of last observation, who do not have a known reason for discontinuation (eg, withdrew consent or AE), and for whom a survival status on the end of trial date cannot be determined will be classified as “lost to follow-up” as the reason for discontinuation. Survival status can be determined from a variety of sources, either by obtaining acceptable documentation for death (ie, death certificate, medical records, public records, statement by a family member or primary care physician) or acceptable documentation for life (ie, direct contact with the subject, medical records, successful telephone contact with the subject, statement by a family member or primary care physician, or public records).

The investigator, subinvestigator, or designee will make 3 documented attempts to contact the subject by telephone, and in the event he/she is unable to reach the subject by telephone, he/she will attempt to contact the subject via certified mail or an alternative similar method, where appropriate, before assigning a “lost to follow-up” status.

The investigator or subinvestigator will record the following items for the subject lost to follow-up in a source document and a CRF.

- Date of investigation
- Investigation method
- Contact with the subject (successful/unsuccessful)
- Reason why the subject does not (cannot) visit
- Presence or absence of AEs. If present, specify its name, dates of onset and resolution, severity, and IMP causality.
- Action taken with the IMP, treatment for the event, and outcome
- If the investigation is impossible, specify the reason

3.12 Legal Representative or Subject Compliance

During the trial period, a subject will be placed under the management of the investigator or subinvestigator. The investigator or subinvestigator will instruct a legal representative and subject to adhere to the following.

- The IMP should be taken according to the specified dose and regimen
- The specified schedule should be followed during the trial period
- Prohibited concomitant medications (see [Section 4.1](#)) should not be used
- The dose and regimen of restricted concomitant medications (see [Section 4.2](#)) should not be changed
- Information obtained as a result of participation in the trial should not be divulged to a third party

3.13 Protocol Deviations

The investigator or subinvestigator must not make deviations from or changes to the protocol without prior written agreement with the sponsor, as well as prior review and written approval by the IRB.

The investigator or subinvestigator may make deviations from or changes to the protocol without prior written agreement with the sponsor or prior review and written approval by the IRB, if the deviations or changes cannot be avoided to eliminate immediate hazards to subjects or for other medical reasons. In such cases, the investigator should promptly submit a document stating the details and reason of deviation or change to the sponsor and the head of the trial site, and obtain approval from the IRB. In addition, the investigator should obtain approval from the head of the trial site and a written agreement from the sponsor through the head of the trial site.

1) Reporting to the sponsor

In the event of a significant deviation from the protocol due to an emergency, accident, or mistake (eg, violation of informed consent process, IMP dispensing or subject dosing error, treatment assignment error, subject enrolled in violation of eligibility criteria or concomitant medication criteria), the investigator, subinvestigator, or designee will contact the sponsor at the earliest possible time by telephone. The investigator or subinvestigator and the sponsor will come as quickly as possible to a joint decision regarding the subject's continuation in the trial. This decision will be documented by the investigator or subinvestigator and the sponsor, and reviewed by the site monitor.

2) Recording deviations

The investigator or subinvestigator will record all deviations from the protocol in a source document.

In addition, the investigator or subinvestigator will record certain specified items of the protocol deviations in a CRF according to the procedures for preparing a CRF provided by the sponsor.

4 Restrictions

4.1 Prohibited Concomitant Medications

If any medication other than the IMP was used from the date of informed consent to the end of trial date, its name, indication, regimen, daily dose, administration route, and start and end dates should be recorded in a source document and a CRF. For therapy other than medication, its name, indication, and start and end dates should be recorded in a source document and a CRF.

Concomitant use of medications and other substances listed in Table 4.1-1 and Table 4.1-2 is prohibited from the pretreatment observation period (3-1 days before start of tolvaptan administration) through the completion of an examination 2 days after final administration. This shall not apply to inevitable cases such as treatment for AEs.

Table 4.1-1 List of Medications Prohibited Before the Trial

 Drugs and foods that may be a strong inhibitors or inducers of CYP3A4 (see Table 4.1-2) Tolvaptan-containing drug products other than the IMP, mozavaptan hydrochloride Drugs unapproved in Japan

Table 4.1-2 Drugs and Foods That May Be a Strong Inhibitors or Inducers of CYP3A4

Drug class	Drug
1) CYP3A4 inhibitors (excluding external agents)	
Antimicrobials	Clarithromycin, erythromycin, fluconazole, itraconazole, miconazole, norfloxacin, chloramphenicol, voriconazole, telithromycin, ciprofloxacin, fosfluconazole, clotrimazole
Calcium antagonists	Diltiazem, verapamil
Therapeutic drugs for gastritis/peptic ulcer	Cimetidine
Immunosuppressants	Cyclosporine
Anticancer drugs	Imatinib, crizotinib

Table 4.1-2 Drugs and Foods That May Be a Strong Inhibitors or Inducers of CYP3A4	
Anti-HIV drugs	Indinavir, nelfinavir, ritonavir, saquinavir, delavirdine, atazanavir, fosamprenavir, lopinavir, darunavir, telaprevir, cobicistat
Autonomic drugs	Tofisopam
Adenosine A2A receptor antagonists	Istradefylline
Antiemetics	Aprepitant
Selective serotonin reuptake inhibitors	Fluvoxamine
2) CYP3A4 inducers (excluding external agents)	
Barbiturates	Phenobarbital, amobarbital, pentobarbital, barbital, secobarbital
Antiepileptics	Carbamazepine, phenytoin
Antitubercular drugs	Rifampicin, rifabutin
Psychostimulants	Modafinil
Anti-HIV drugs	Efavirenz, nevirapine, etravirine
Endothelin receptor antagonists	Bosentan
Anticancer drugs	Enzalutamide
Corticosteroid synthesis inhibitors	Mitotane
3) Foods containing substances that inhibit CYP3A4	Grapefruit, Seville orange, star fruit, and their processed products
4) Foods containing substances that induce CYP3A4	Foods containing St. John's wort

HIV = human immunodeficiency virus

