4.2 Restricted Concomitant Medications

The dose and regimen of the following medications should not be changed from the pretreatment observation period through the completion of an examination 2 days after final administration in principle. Change of dose and regimen during this period is allowed if it is required for safety reasons. In such cases, “the reason of change” and “the details of change” should be recorded. Within 24 hours before and after first tolvaptan administration, however, the dose and regimen of restricted concomitant medications should not be changed (if changed, the subject’s participation in the trial should be discontinued).

- Therapeutic drugs for heart failure (injectables): Catecholamine preparations, human atrial natriuretic peptide preparations, phosphodiesterase 3 inhibitors, colforsin preparations, etc
- Diuretics (oral preparations and injectables)

5 Reporting of Adverse Events

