7.1 Sample Size

For the primary endpoint, the required sample size was set by first setting the threshold value for assessment of efficacy, and then using binomial distribution to determine the number of subjects required to maintain a 90% or higher probability that the lower limit of the 95% CI for the percentage of subjects achieving the primary endpoint will be above the threshold value.

As reference information for the threshold value and binomial distribution parameter required to set the sample size for the trial, a threshold of 0.3 and a binomial distribution parameter of 0.5 to 0.6 were used based on interviews with clinicians, since no clinical trial results for administration of tolvaptan in pediatric patients have been obtained either in Japan or other countries.

Based on the above, the required number of subjects was calculated to be a minimum of 68 for a parameter of 0.5 and a minimum of 30 for a parameter of 0.6.

A sample size of 30 to 68 subjects was therefore considered to be appropriate, and in view of feasibility the number of subjects for the trial was set at 60.

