## **6 Primary and Secondary Outcome Variables:**

### **6.1 Primary Outcome Variables**

The percentage of subjects who satisfy the following condition:

- Body weight on the day after the third day of treatment with tolvaptan at the evaluation dose (see [Section 7.4](#)) is decreased by 1.7% or more from the weight measured before breakfast on the first day of the treatment period

However, mean daily urine volume for the 3 days of treatment with tolvaptan at the evaluation dose must be higher than the daily urine volume for the pretreatment observation period. For subjects whose treatment period at evaluation dose is less than 3 days, mean daily urine volume at the time of the treatment at evaluation dose must be higher than the daily urine volume for the pretreatment observation period.

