## 7.5            Prior and Concomitant Medications

For the full analysis set and safety analysis set, frequency distributions for usage of concomitant medication on the initial IMP administration day will be calculated.

Table 7.5-1      Usage of Concomitant Medication on the Initial IMP Administration Day	
Variable	Level
Category of diuretic *Concomitant use of diuretic drugs other than loop diuretic, thiazide diuretic, and anti-aldosterone drug is not summarized.	Monotherapy with loop diuretic, Loop diuretic + thiazide diuretic, Loop diuretic + anti-aldosterone drug, Loop diuretic + thiazide diuretic + anti-aldosterone drug
Thiazide diuretic	No, Yes
Anti-aldosterone drug	No, Yes
Drugs for heart failure other than diuretics	No, Yes
CYP3A4 inducers	No, Yes
CYP3A4 inhibitors	No, Yes

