### **8.2.2.2 Edema (Eyelids), Jugular Venous Distension, Dyspnea, and Pleural Effusion**

A shift table will be prepared for changes in the degree of edema (eyelids), jugular venous distension, and dyspnea from baseline to the third day of administration at the evaluation dose, the day of the final administration at the evaluation dose, and the day of the final administration. Another shift table will also be prepared for each time point after the start of administration at the evaluation dose. Analysis will also be performed using

data collected immediately before the start of administration at the evaluation dose as the baseline. In addition, data will be summarized by the number of days elapsed since the start of administration.

The number and percentage of subjects as well as the exact 95% CI based on the binomial distribution will be calculated for the disappearance rate on the third day of administration at the evaluation dose, the day of the final administration at the evaluation dose, and the day of the final administration. Analysis will also be performed using data collected immediately before the start of administration at the evaluation dose as the baseline.

A shift table will be prepared for changes in the degree of pleural effusion from baseline through the day after the final administration.

The number and percentage of subjects as well as the exact 95% CI based on the binomial distribution will be calculated for the disappearance rate on the day after the final administration.

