**Appendix 2****List of Subject Data Listings**

DREAS-1	Discontinued Subjects and Reason for Discontinuation (IMP Administered Subjects)
SUBEX-1	Subjects Excluded From Analysis Set (IMP Administered Subjects)
DEMOG-1	Demographic and Baseline Characteristics (IMP Administered Subjects)
SMED-1	Investigational Medicinal Product Compliance (IMP Administered Subjects)
PDEV-1	Protocol Deviations (IMP Administered Subjects)
AE-1	Adverse Events (IMP Administered Subjects)
AE-2	Adverse Events Observed Before Start of Investigational Medicinal Product Administration (IMP Administered Subjects)
LAB-1	Laboratory Test Results - Serum Chemistry (IMP Administered Subjects)
LAB-2	Laboratory Test Results - Hematology (IMP Administered Subjects)
LAB-3	Laboratory Test Results - Urinalysis (IMP Administered Subjects)
PDATA-1	Study Completion Status and Reason for Discontinuation (IMP Administered Subjects)
PDATA-2	Inclusion Criteria and Exclusion Criteria Not Met (Screened Subjects)
PDATA-3	Medical History and Complications (IMP Administered Subjects)
PDATA-4.1	Concomitant Medications (IMP Administered Subjects)
PDATA-4.2	Concomitant Therapy Other Than Medication (IMP Administered Subjects)
PDATA-5	Vital Signs (IMP Administered Subjects)
PDATA-6	Electrocardiogram Results (IMP Administered Subjects)
PDATA-7	Pharmacokinetic Blood Draw Time (IMP Administered Subjects)
PDATA-8	Screen Failures
PDATA-9	Serum Sodium Concentration, Serum Potassium Concentration (IMP Administered Subjects)
PDATA-10	Serum Osmolality, Plasma AVP Concentration (IMP Administered Subjects)

- PDATA-11 Daily Urine Volume, Daily Fluid Intake, Daily Fluid Balance (IMP Administered Subjects)
- PDATA-12 Urine Sodium Concentration, Urine Osmolality, Urine Potassium Concentration, Daily Urine Excretion of Sodium and Potassium (IMP Administered Subjects)
- EFF-1 Body Weight (IMP Administered Subjects)
- EFF-2 Congestive Symptoms (Lower Limb Edema, Eyelids Edema, Dyspnea, Juglar Venous Distension, Respiration Rate at Rest, Pulse Rate, Pleural Effusion) (IMP Administered Subjects)
- EFF-3 Congestive Symptoms (Other Edema) (IMP Administered Subjects)
- EFF-4 Chest X-ray (Pulmonary Congestion, Cardiothoracic Ratio) (IMP Administered Subjects)
- EFF-5 Congestive Symptoms (Central Venous Pressure) (IMP Administered Subjects)
- EFF-6 Congestive Symptoms (Retention of Pericardial Effusion) (IMP Administered Subjects)

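### No efficacy rule covers fluid-removing procedures: a child drained during treatment can count as a responder if urine volume also rises, and a drained pleural effusion counts as resolved

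*Protocol*

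**What the plan says.** Protocol 4.1 prohibits certain CYP3A4 inhibitors and inducers, other tolvaptan products, mozavaptan, and drugs unapproved in Japan. Protocol 4.2 holds two groups constant: diuretics, oral or injectable, and a class beginning "Therapeutic drugs for heart failure (injectables): Catecholamine preparations, human atrial natriuretic peptide preparations". Procedures appear in neither list. Protocol 4.1 says of them: "For therapy other than medication, its name, indication, and start and end dates should be recorded in a source document and a CRF". Protocol 3.8.3.1 mentions a disallowed therapy in passing, but no therapy is named as disallowed.

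SAP 6.1 defines a responder by body weight on the day after the third day at the evaluation dose, which must be "decreased by 1.7% or more from the weight measured before breakfast on the first day of the treatment period". Mean daily urine volume at that dose must also be higher than in the pretreatment observation period.

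SAP 8.2.2.1 defines the disappearance rate as the share of children with the symptom at baseline in whom it had resolved after dosing. SAP 8.2.2.2 applies that rate, with an exact interval, to pleural effusion, and adds: "A shift table will be prepared for changes in the degree of pleural effusion from baseline through the day after the final administration". Pericardial effusion is only listed (SAP 8.2.2.5).

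Non-drug therapy appears in the SAP only as listing PDATA-4.2 in Appendix 2. The serious-deviation classes in SAP 7.6 have no category for procedures.

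**The concern.** The trial is uncontrolled, so any weight lost during treatment is read as an effect of tolvaptan. A weight taken after a drain is not missing, so the imputation rules in SAP 5.6 do not touch it and it is scored as measured. Daily fluid balance is intake minus urine (Protocol 3.7.4.2.2), so drained volume enters no derived variable.

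For fluid removal the error favours the drug in the responder rate, percent weight change and the pleural effusion disappearance rate, and may do so in the cardiothoracic ratio. Pleural effusion is a secondary endpoint, and Protocol 3.7.2.6 provides for children with excessive pericardial effusion, so the plan allows for patients in whom drainage is conceivable.

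**Working it through.** **1. The exposure window.** Weight is compared between Day 1 and the day after the third evaluation-dose day. Under the titration steps in Protocol 3.2.2, without dose reduction, the third day at each step is Day 3, 5, 7 or 9. The endpoint weight therefore falls on Day 4, 6, 8 or 10.

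**2. What the urine condition does.** It requires a mean above one pretreatment day; any increase passes. Under Protocol 3.2.2 a child who stopped escalating below the top step because the response was sufficient has had at least one day at 150% or more of the pretreatment volume. The condition shows that diuresis occurred. It does not show that diuresis produced the 1.7% loss.

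**3. Volume that meets the weight criterion alone.** With 1 g = 1 mL (the conversion that Protocol 3.7.2.2 uses for diapers), 1.7% of 1 kg is 0.017 × 1000 = 17 mL. Illustrative weights:

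| Body weight | 17 mL/kg |
|---|---|
| 5 kg | 85 mL |
| 10 kg | 170 mL |
| 20 kg | 340 mL |
| 40 kg | 680 mL |

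A child who has lost 0.7% by other means needs only 1.7 − 0.7 = 1.0%, or 10 mL/kg.

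**4. The plan's own sample size.** Protocol 7.1 takes "a threshold of 0.3 and a binomial distribution parameter of 0.5 to 0.6 were used based on interviews with clinicians" and seeks the "number of subjects required to maintain a 90% or higher probability that the lower limit of the 95% CI" is above that threshold. With the exact (Clopper-Pearson) interval:

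- At 0.5 the probability is 0.912 at n = 66, 0.889 at n = 67 and 0.909 at n = 68, and it stays at or above 0.90 from 68.
- At 0.6 it is first reached, and then held, at n = 30 (0.903).

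Both stated figures, 68 and 30, are reproduced.

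**5. Rule at the planned n = 60.** The exact lower limit is 29.1% with 25 responders and 30.6% with 26, so at least 26 are needed. One child is 1/60 = 1.7 percentage points.

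**6. Effect of a few drained children.** Let *m* children be certain responders and the other 60 − *m* respond independently at true rate *p*. The chance of success is P[Bin(60 − *m*, *p*) ≥ 26 − *m*]:

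| True rate | m = 0 | m = 1 | m = 2 | m = 3 |
|---|---|---|---|---|
| 0.30 (threshold) | 2.0% | 2.9% | 4.3% | 6.2% |
| 0.40 (not a planning value) | 34% | 40% | 46% | 53% |
| 0.50 (planning) | 87.7% | 90.4% | 92.6% | 94.4% |
| 0.60 (planning) | 99.7% | 99.8% | 99.9% | 99.9% |

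The value of *m* is an assumption, because the documents give no procedure frequency. Each of the *m* children is taken to meet the urine condition.

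**7. Pleural effusion.** The baseline film is taken in the pretreatment observation period. A child with effusion then, drained afterwards and clear on the post-dose film, meets the SAP 8.2.2.1 definition. No exception is written.

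**The case against.** The strongest reply is that the primary endpoint is not weight alone. The urine condition was added because weight can change for other reasons (Protocol 3.5.2), and it removes a drained child who had no diuresis. That stands: drained weight does not count as a response by itself. But any increase over one day is enough, so the guard is partial.

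The effect is also small where the drug works as hoped: at 0.60 nothing changes materially. The steepest rise is at 0.40, which the plan does not use. The 0.3 threshold appears only in the sample-size text, and efficacy is to be judged comprehensively, so crossing it is not a formal decision rule. All of this stands and limits the size of the point.

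Some protection exists. Children improving before dosing are excluded, the investigator may withdraw a child, and the individual weight plots (CF-1.1) read beside PDATA-4.2 could show a step loss on a procedure date. The analysis from the start of the evaluation dose shortens the window for children titrated upward. None of these changes how a drained child is scored in the primary table.

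Four stronger readings are tempting and not supported:

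- **Oral heart-failure drugs.** A reader might extend the point to these, since SAP 7.5 tabulates "Drugs for heart failure other than diuretics" only on the first dosing day. Oral diuretics are already restricted, and nothing in the documents shows that starting another oral agent would remove 1.7% of body weight within days.
- **All drained effusions.** Only pleural effusion has a disappearance rate. Pericardial effusion is listed, and ascites is not an endpoint.
- **Blood purification.** Exclusions for assisted circulation, CKD Stage 3 or higher and anuria make it a weak example.
- **A one-sided bias from all unrestricted therapy.** Hypotonic solution and transfusion, which the protocol mentions, can add weight. The direction claimed here applies to fluid removal only.

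**Conclusion.** The point holds as a limited gap in the analysis plan. Followed exactly, the plan scores a post-drain weight as measured, makes the child a responder if mean urine volume also rose, and counts a drained pleural effusion as resolved. In an uncontrolled trial nothing offsets this.

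A single drained child moves the responder rate by at most 1.7 points. One to three such children raise the chance of clearing the threshold by 0.9 to 4.2 points at a true rate of 0.30 (2.0% to 2.9–6.2%) and by 2.7 to 6.7 points at 0.50 (87.7% to 90.4–94.4%). These figures rest on an assumed number of drained children, on each meeting the urine condition, and on each becoming a certain responder. Whether any such child will occur cannot be learned from the documents, so the bias is possible but not shown to be material. The planned main analysis can stand; what is missing is a prespecified check on it.

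**What to change.** 1. **SAP 8.1.1.** Add a supportive run of table CT-5.1.1. Count as a non-responder any child with a recorded fluid-removing procedure dated from Day 1 through the day of the endpoint weight, unless a weight measured before the procedure date already met the 1.7% criterion. Treat a procedure dated on a weighing day as inside the window, because the protocol requires only dates, not times, for non-drug therapy. Report the number of such children with the table.
2. **SAP 8.2.2.2.** Count a pleural effusion drained after the baseline assessment and before the post-dose assessment as not resolved.
3. **SAP 8.2.2.3.** Flag the cardiothoracic ratio of any such child.

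The cost is SAP wording and one extra table, built from therapy names and dates already on the CRF. The supportive responder rate may be slightly lower, by 1.7 points per reclassified child at n = 60, and so may the disappearance rate. The main primary analysis, sample size and trial conduct are unchanged, and no change to clinical management is proposed. If no child was drained, one sentence saying so settles the matter.
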